Right ventricular (RV) failure is the most common cause of death in pulmonary arterial hypertension (PAH). No RV-specific therapies are available, in part because the underlying mechanisms of RV failure are poorly understood. A growing body of evidence suggests that metabolic abnormalities may underlie RV dysfunction in PAH. Interventions against metabolic dysfunction in PAH may protect against RV failure. We have identified abnormalities in fatty acid (FA) metabolism in PAH that overlap considerably with disorders of carnitine deficiency. Carnitine links to an acyl group, which is required to transport FAs across the mitochondrial membrane to undergo beta-oxidation, the predominate source of ATP production in the human heart. Inborn errors of carnitine metabolism and acquired carnitine deficiency are associated with cardiomyopathy. Acquired deficiency primarily occurs via binding of carnitine to excess circulating fatty acids or renal wasting. Carnitine deficiency and PAH are both associated with insulin resistance, myocardial lipotoxicity, and mitochondrial oxidative stress. Carnitine supplementation in humans and animal models of cardiometabolic dysfunction reverses these abnormalities but has not been studied in PAH. In published work, we found that in RV samples from humans with PAH, there is a marked (up to 300-fold) reduction in acylcarnitines along with increased long-chain fatty acids. We also a found a two-fold increase in circulating fatty acids FAs in humans with PAH, indicating increased delivery to the myocardium. As a consequence of unchecked fatty acid accumulation, we observed 7-fold higher RV lipid content and markers of lipotoxicity. These observations suggest there is inadequate carnitine substrate to bind fatty acids and facilitate their transport across the mitochondrial membrane in the human PAH RV.

Our overarching hypothesis is that in human PAH, RV function can be improved by augmenting carnitine substrate availability to improve outcomes. In preparation for a future mechanistic study, we now propose to test the specific hypothesis that carnitine consumption is not reduced in PAH, that plasma carnitine levels are stable over time in PAH and that carnitine supplementation in PAH can increase plasma carnitine and thereby delivery of carnitine to the RV and possibly improve RV function. We propose three aims in humans to test this mechanistic hypothesis, 1) Measure the oral consumption of carnitine in human PAH. This aim will use food diaries and carnitine supplement use questionnaires in PAH patients to test the hypothesis that carnitine supplementation is uncommon in PAH and food consumption is adequate. Aim 2) Measure the stability over time in plasma carnitine levels in PAH patients. This aim will test the hypothesis that plasma carnitine is not affected by disease severity and is stable over time in PAH patients. We will measure plasma carnitine concentration and markers of fatty acid oxidation at Visit 1 and Visit 2. 3) Perform a mechanistic pilot study using carnitine supplementation to enhance circulating carnitine in PAH. This small pilot study will test the hypothesis that carnitine supplementation increases plasma carnitine (primary endpoint) and will test for physiologic effects using six minute walk testing, echocardiography and plasma markers of lipid metabolism.

Protocol Summary

OBJECTIVES: The primary objective of this study is to evaluate the effect of standard L-carnitine supplementation in PAH patients on plasma carnitine levels. Secondary objectives include: to measure the oral consumption of carnitine in human PAH to measure the stability over time in plasma carnitine levels in PAH patients **STUDY DESIGN:** This is a single-center, prospective study enrolling 10 PAH patients. All eligible participants will be given carnitine supplements for 2 weeks. **STUDY POPULATION:** Inclusion criteria: Adults aged 18 or older. • Diagnosed with idiopathic, heritable, simple congenital • heart disease, or drug- or toxin-associated pulmonary arterial hypertension (PAH) according to World Health Organization consensus recommendations. Stable PAH-specific medication regimen for three • months prior to enrollment. Subjects with only a single diuretic adjustment in the prior three months will be included. Adjustments in IV prostacyclin for side effect management are allowed. FEV1> or = 60% predicted and no more than mild • abnormalities on lung imaging WHO Functional Class I-III Ambulatory • **Exclusion criteria:** Prohibited from normal activity due to wheelchair bound status, bed bound status, reliance on a cane/walker, activity-limiting angina, activity-limiting osteoarthritis, or other condition that limits activity Pregnancy • Diagnosis of PAH etiology other than idiopathic, • heritable, simple congenital heart disease, or associated with drugs or toxins

• Drug and toxin associated PAH patients with active drug use

- Prior diagnosis of cirrhosis
- Malignancy
- eGFR by MDRD <60mL/min
- Known allergy to carnitine

PRIMARY ENDPOINT:

SECONDARY ENDPOINTS:

- Difference in plasma carnitine concentration from Visit 1 to Visit 2 and Visit 3 to Visit 4.
- Quantify the prevalence of carnitine supplement use and measure oral ingestion of carnitine in PAH patients.
- Correlation of carnitine ingestion with six-minute walk test.
- Correlation of carnitine ingestion with functional class.
- Correlation of carnitine ingestion with plasma BNP.
- Difference in plasma carnitine concentration from Visit 1 to Visit 2.
- Correlation of plasma carnitine concentration with TMAO concentration.
- Difference in plasma acylcarnitines from Visit 1 to Visit 2.
- Difference in lipid metabolites from Visit 1 to Visit 2.
- Difference in RV function with L-carnitine supplementation.
- Difference in plasma carnitine concentration from Visit 1 to Visit 2.
- Difference in plasma acylcarnitine profile from Visit 3 to Visit 4.
- Difference in lipid metabolites from Visit 3 to Visit 4.
- Correlation of change in plasma carnitine with change in Functional class.
- Correlation of change in plasma carnitine with change in six-minute walk distance.
- Correlation of change in plasma carnitine with change in BNP.
- Correlation of change in plasma carnitine concentration with TMAO concentration
- Correlation of change in plasma carnitine with change in markers of RV function including TAPSE and RV fractional area change.
- Markers of tolerability including presence of side effects, adverse events and serious adverse events.
- Pill counts at Visit 4 for adherence.

STUDY OBSERVATIONS:

- Subjects will be evaluated in person at Visit 1, Visit 2, Visit 3, and Visit 4.
- BNP, carnitine assay, lipid metabolites, carnitine, acylcarnitine, and other biomarkers will be assessed at Visit 1, Visit 2, Visit 3, and Visit 4.
- Subjects will have six-minute walk testing at Visit 1, Visit 2, and Visit 4.
- Subjects will have a transthoracic echocardiogram at Visit 2 and Visit 4.
- Subjects will submit food and supplement diary at Visit 1, Visit 2, and Visit 4.

SAMPLE SIZE AND POWER:

In a study of 28 PAH patients⁶ the mean \pm SD of plasma carnitine data was 38.6±11.1 uM. The data appeared to be normally distributed. In a pilot study²¹, L-carnitine supplementation increased free plasma carnitine concentration by 22% (Table 3 in²¹). A sample size of 10 will have 80% power to detect a within subject change in means of 8.5 (increase from Visit 1 mean of 38.6 to 47.1 after 2 weeks of treatment, representing a 22% increase) using a paired t-test with a 5% two-sided significance level. The standard deviation of within-subject differences is assumed to be 8.6 and it is calculated using SD of 11.1 assuming a moderate within-subject correlation 0.7. We plan to study 10 PAH patients in this proof-of-concept study. The study has 80% power to detect a within-subject change of effect size 1, i.e. change measured as 1 times of the SD.

DATA ANALYSIS:

The primary endpoint and other continuous endpoints will be summarized using the mean, standard deviation, the median, and interquartile range. We will use either the paired t-test or the Wilcoxon-signed rank test to assess the change from Visit 1 on these endpoints. Estimate of mean change along with its 95% confidence interval will be reported to quantify the treatment effect. To assess tolerability of carnitine, we will closely monitor any adverse events. For these binary events, proportion of subjects who experience the event will be calculated along with its 95% confidence interval. We will use the open-source statistical package R⁴⁸ for analyses.

1 Background & Significance

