3.3 Supplement Dosing

A 14-19-day supply of Carnitine supplements will be provided to the subject at Visit 2. The VUMC Pharmacy for Research will supply Nature's Bounty L-Carnitine 500mg caplets to be taken by mouth. For subjects weighing <90kg, I- carnitine will be taken at 1.5g twice a day. For subjects weighing >90kg, I-carnitine will be taken at 50 mg/kg/day split between 2 doses. Dosing for these participants will be rounded to the next whole pill to achieve approximately 50 mg/kg per day. Dosing will be incrementally titrated by 25- 50% in the event of intolerance and/or side effects limiting subject's compliance to prescribed regimen.

4 Data Collection

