4.2.4 Study Day – Visit 2 (Week 12)

All tests done at the Visit 1 visit will be repeated at the Visit 2 Visit. The following procedures will be performed:

- review of interim medical history
- review of current medications
- WHO functional class
- blood collection
- urine pregnancy test (as necessary)
- symptom assessment
- vital signs
- physical exam
- review of food and supplement diary (ASA24)
- six-minute walk test
- transthoracic echocardiography
- Dosing of Carnitine supplement

After fasting research labs have been drawn, the subject will have the opportunity to eat a snack. The investigator or research nurse will take an interim medical history, perform a physical examination including checking vital signs, and review current medications. The subject will perform the six-minute walk test. An experienced research sonographer will perform the transthoracic echocardiography.

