4.2.5 Study Day- Visit 3 (Week 12+1 day)

The day following Visit 2, a brief visit will be performed with the following procedures:

- blood collection
- symptom assessment
- vital signs
- review of food and supplement diary (ASA24)
- 2 weeks supply of carnitine supplement provided

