5.1 Assessments of Efficacy

Primary Endpoint: Difference in plasma carnitine concentration from Visit 1 to Visit 4.

Secondary Endpoints:

- Quantify the prevalence of carnitine supplement use
- Measure oral ingestion of carnitine in PAH patients.
- Difference in six-minute walk test from Visit 1 to Visit 2.
- Difference in functional class from Visit 1 to Visit 2.
- Difference in plasma BNP from Visit 1 to Visit 2
- Difference in plasma carnitine concentration from Visit 1 to Visit 2.
- Correlation of plasma carnitine concentration with TMAO concentration.
- Difference in plasma acylcarnitines from Visit 1 to Visit 2.
- Difference in lipid metabolites from Visit 1 to Visit 2.
- Change in plasma carnitine from Visit 2 to Visit 3.
- Difference in RV function from Visit 2 to Visit 4.
- Difference in plasma acylcarnitine profile from Visit 2 to Visit 4.
- Difference in lipid metabolites from Visit 2 to Visit 4.
- Correlation of change in plasma carnitine with change in Functional class.
- Correlation of change in plasma carnitine with change in six minute walk distance.
- Correlation of change in plasma carnitine with change in BNP.
- Correlation of change in plasma carnitine concentration with TMAO concentration
- Correlation of change in plasma carnitine with change in markers of RV function including TAPSE and RV fractional area change.
- Markers of tolerability including presence of side effects, adverse events and serious adverse events.

- Pill counts at Visit 4 for adherence
- 5.2 Secondary Outcome Measures

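### The synopsis starts its supplement-period contrasts at Visit 3, which is probably already an on-supplement sample; they should start from an untreated visit, as Section 5.1 does

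*Combined protocol and SAP*

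**What the plan says.** **Synopsis endpoints.** The Protocol Summary gives three supplement-period contrasts that begin at Visit 3:

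- carnitine: "Difference in plasma carnitine concentration from Visit 1 to Visit 2 and Visit 3 to Visit 4"
- acylcarnitines: "Difference in plasma acylcarnitine profile from Visit 3 to Visit 4"
- lipids: "Difference in lipid metabolites from Visit 3 to Visit 4"

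**Body endpoints.** Section 5.1 sets the primary endpoint as the carnitine difference between Visit 1 and Visit 4. It lists "Change in plasma carnitine from Visit 2 to Visit 3" as a separate secondary endpoint. For acylcarnitines it has "Difference in plasma acylcarnitine profile from Visit 2 to Visit 4", and lipid metabolites get the same pair of visits.

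**Analysis and power.** The data analysis text (Protocol Summary and Section 6.2) tests change from Visit 1. The power calculation (Protocol Summary and Section 6.1) starts from a Visit 1 mean of 38.6 uM.

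**Start of supplementation.** Section 3.3 says: "A 14-19-day supply of Carnitine supplements will be provided to the subject at Visit 2". Section 4.2.4 lists "Dosing of Carnitine supplement" among the Visit 2 procedures. Section 4.2.5 introduces Visit 3 with "The day following Visit 2, a brief visit will be performed with the following procedures", and that list includes handing over a two-week supply.

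**The concern.** A within-subject change measures the effect of a supplement only if its first sample is untreated. This trial has ten patients and no control arm, so the choice of baseline sample carries the whole estimate. If carnitine is first taken at Visit 2, the Visit 3 sample already contains part of the response, and the synopsis contrast removes that part from the effect. Plasma carnitine is also the subject of the primary objective.

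The endpoint lists also disagree. For the effect of supplementation on carnitine, the synopsis starts at Visit 3 and Section 5.1 at Visit 1. For acylcarnitines and lipids, the synopsis starts at Visit 3, Section 5.1 at Visit 2, and the general statement in Section 6.2 at Visit 1. No text says which list prevails, so the contrast could be chosen after the data are seen.

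**Working it through.** **1. Is Visit 3 an untreated sample?**

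Pointing to a first dose at Visit 2:
- Section 3.3 provides the supply at Visit 2.
- Section 4.2.4 lists dosing as a Visit 2 procedure.
- Table 1 marks the supplement from Visit 2 and checks compliance at Visit 3.
- Section 5.1 treats the change from Visit 2 to Visit 3 as an endpoint of its own, which tells us about supplementation only if a dose falls between the two samples.

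Pointing to a start at Visit 3:
- Section 4.2.5 provides a two-week supply at Visit 3.
- Section 4.2.6 places the Week 13 call one week after supplementation begins. Table 1 puts that call at Day 92 and Visit 4 at Day 99. Counted from Visit 3 (Day 85) these are 92 − 85 = 7 and 99 − 85 = 14 days; from Visit 2 (Day 84) they are 8 and 15. Both carry a window of 5 days either way, so the count is only weak evidence.

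The first group weighs more, but the conflict is real. Visit 3 is probably, not certainly, on supplement.

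**2. Would a first-day rise still be there?** Section 1.5 puts the plasma peak 3 to 6 hours after an oral dose. The plan gives neither a day-1 concentration nor the time between dose and Visit 3 sample. The fraction remaining, f, is therefore unknown and may be zero.

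**3. Reproduce the plan's power.** Inputs from Section 6.1: n = 10, change 8.5 uM, SD 11.1, correlation 0.7, two-sided 5%.

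- Change: 0.22 × 38.6 = 8.49, stated as 8.5.
- SD of differences: 11.1 × √(2 × (1 − 0.7)) = 8.598, stated as 8.6.
- Noncentrality: (8.5 / 8.6) × √10 = 3.13, with 9 degrees of freedom and critical t = 2.262.
- Power from the noncentral t: 79.4%, which matches the stated 80%.

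**4. Illustrate a Visit 3 baseline.** Replace the change by 8.5 × (1 − f) and hold the SD at 8.6.

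| f (assumed) | Change, uM | Power, n = 10 |
|---|---|---|
| 0% | 8.50 | 79.4% |
| 10% | 7.65 | 70.7% |
| 25% | 6.38 | 55.2% |
| 50% | 4.25 | 28.8% |

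**5. Sensitivity to the SD.** The 8.6 comes from a calculation based on Visit 1, and nothing in the plan supports carrying it to two samples two weeks apart that may both be on supplement. With correlation 0.6 the SD is 11.1 × √0.8 = 9.93; with 0.8 it is 11.1 × √0.4 = 7.02. At f = 10% power is then 58% or 86%; at f = 25% it is 44% or 72%. The table shows a direction and a range, not an estimate.

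**6. Which baseline is safe?** If dosing starts at Visit 2, the Visit 2 blood is the last untreated sample, provided it is drawn before the dose; Section 4.2.4 lists blood collection ahead of dosing. If dosing starts only after the Visit 3 sample, Visit 2 is untreated anyway. Visit 2 to Visit 4 is valid on either reading; Visit 3 to Visit 4 is valid on one.

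**The case against.** The strongest reply is that nobody following the body of the plan would use Visit 3 as a baseline. Section 5.1, the analysis text in both places and the power calculation all start from untreated visits. This stands: the fault is confined to the synopsis endpoint list and the conflict it creates.

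A reader might infer more, and four stronger readings are not supported.

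- *Visit 3 is definitely post-dose.* Sections 4.2.5 and 4.2.6 and the day count in Table 1 leave room for a start at Visit 3.
- *The primary result is biased towards zero.* The primary endpoint in Section 5.1 is Visit 1 to Visit 4. In the available text the synopsis heading for the primary endpoint is empty and the carnitine item sits under the secondary endpoints. It may have been displaced when the text was extracted, so its rank cannot be settled and no error is claimed from it.
- *All three effects are understated.* The plan gives no day-1 change for acylcarnitines or lipids, so no direction can be assigned to them.
- *The trial loses a known amount of power.* The fraction f and the carried-over SD are both assumptions, and the plan never powers a Visit 3 to Visit 4 contrast.

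**Conclusion.** The point holds as an inconsistency that needs correcting, not as a flaw in the sampling design. The synopsis takes as its baseline a sample that is probably on supplement, and it contradicts Section 5.1 on all three analytes. If the synopsis were followed, the carnitine effect would be understated by whatever first-day rise persists at Visit 3; the effect on acylcarnitines and lipids could be distorted in either direction. The size is not derivable. The illustrative fall in power from 79% to between 71% and 29% assumes that 10% to 50% of the rise is present at Visit 3 and that the SD of differences stays at 8.6; with none present there is no loss. An analysis that follows Sections 5.1 and 6.2 is free of a Visit 3 baseline.

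**What to change.** 1. In the Protocol Summary, replace each Visit 3 to Visit 4 contrast with one that starts from an untreated visit. For the acylcarnitine profile and lipid metabolites, use Visit 2 to Visit 4, as Section 5.1 does.
2. For plasma carnitine, choose one untreated-baseline contrast and state it identically in the synopsis, Section 5.1 and Section 6.2. Changing the synopsis alone to Visit 2 to Visit 4 would leave it in conflict with the Visit 1 to Visit 4 primary endpoint in 5.1.
3. In Section 6.2, name the baseline visit for each endpoint, because its general change from Visit 1 does not match the Visit 2 to Visit 4 endpoints in 5.1.
4. Keep Visit 3 for the early-response endpoint (Visit 2 to Visit 3), and state that it is not a baseline for any supplement contrast.
5. Reconcile Sections 3.3, 4.2.4, 4.2.5, 4.2.6 and Table 1 on when supplementation starts, and state whether the Visit 2 and Visit 3 bloods are drawn before or after a dose.

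The cost is wording only. Blood for all three analytes is already scheduled at every visit, so no sample, visit or patient is added.

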1.1 RV Failure in Pulmonary Arterial Hypertension

PAH is a progressive and incurable disease characterized by obliteration of the pulmonary vasculature, elevated pulmonary vascular resistance (PVR), and eventual right ventricular (RV) failure often within 7-10 years of diagnosis¹. Mortality in patients with PAH predominantly results from RV failure and its complications². However, no RV-specific therapy exists because the underlying determinants of RV failure are poorly understood. The importance of targeting RV function directly is highlighted by the observation that outcomes in PAH more closely mirror changes in RV function than pulmonary hemodynamics³. Identification of additional molecular contributions to RV failure in PAH would advance the pursuit of RV-specific therapies and carnitine supplementation holds promise to improve RV function in this deadly disease.

1.2 PAH As A Systemic Metabolic Disease with RV Manifestation

PAH is associated with systemic abnormalities in glucose and lipid metabolism. The first clue in humans was a study showing that patients with PAH have an elevated triglyceride to high density lipoprotein ratio, a marker of insulin resistance. Subsequently, we found a prevalence of almost 60% of unrecognized glucose intolerance in our PAH patients, independent of body mass index (BMI)⁴. The lack of an association with BMI suggests that the mechanism of insulin resistance in PAH may be unrelated to increased adiposity, per se. In addition, we found elevated plasma free fatty acids and long-chain acylcarnitines in humans with PAH compared with matched controls (see Preliminary Data)⁵. More recently, we showed that insulin resistance in PAH specifically involves the lipid axis and is detected through peripheral blood abnormalities in triglycerides and lipid metabolism⁶. While many organs may be affected by insulin resistance, the RV is highly reliant on fat metabolism and thus susceptible to metabolic disorders. We have previously published that the RV in humans with PAH, both alive and at autopsy, has enhanced lipid content^{5.7}. We have also demonstrated that this lipotoxicity is due to increased lipid import via CD36 and reduced fatty acid oxidation in cardiomyocytes⁸. We also demonstrated in human samples an increase in plasma free fatty acid delivery to the PAH RV and a marked (100-300 fold) reduction in myocardial long-chain acylcarnitine concentration, suggesting reduced fatty acid oxidation⁵. These findings provide strong evidence that metabolic dysregulation, and specifically lipid metabolism. is an important feature of PAH and that the RV appears impacted by this altered metabolism.

1.3 Carnitine Metabolism in Health and Disease: Focus on the heart

Carnitine is a nutrient required for the transport of long-chain fatty acids as acylcarnitines across the mitochondrial membrane to undergo beta-oxidation and subsequent ATP production⁹. Carnitine is particularly abundant in skeletal muscle and the myocardium, where fatty acids are the predominant substrate for energy production¹⁰. The presence of adequate carnitine in myocardial cells is essential for normal fatty acid metabolism. Reduced availability of carnitine from any cause leads to impaired fatty acid oxidation and muscle dysfunction. When carnitine binds fatty acids, acylcarnitines are formed and then normally undergo beta-oxidation. In conditions of excess circulating free fatty acids (e.g. diabetes and heart failure), acylcarnitines are formed in excess of mitochondrial oxidative capacity. This results in a depletion of carnitine, reduced fatty acid oxidation, oxidant stress, and accumulation of toxic lipids. Excess acylcarnitines are excreted from cells and elevated levels can be detected in the plasma in conditions of abnormal

carnitine metabolism⁹. Oleovicarnitine and three other long-chain acvicarnitines are strongly associated cardiovascular mortality in a dialysis population¹¹; the same four acylcarnitines were most elevated in our PAH population compared to healthy subjects⁵. Cardiomyocytes cannot synthesize carnitine, which must be acquired exogenously. Thus, deficiencies, even relative, in carnitine have particularly adverse effects in cardiomyocytes. Inborn errors of carnitine metabolism involve abnormal transporter function and present with severe, often fatal, cardiomyopathy¹². Secondary carnitine deficiency occurs because the available carnitine is bound to excess fatty acids or due to renal wasting¹³. Acquired carnitine deficiency has been described in dialysis therapy, diabetes, and heart failure, among other conditions¹⁴⁻¹⁶. Chronic carnitine deficiency is associated with insulin resistance. lipid-induced cardiomyopathy, and increased mitochondrial oxidative stress¹⁶. Carnitine supplementation in humans and experimental models appears to mitigate these defects. In humans with heart failure, carnitine improves diastolic and systolic dysfunction and may reduce cardiovascular events^{15,17}. In diabetics, carnitine reduces myocardial free FA uptake and circulating long-chain acylcarnitines. In mice exposed to doxorubicin, carnitine reduces ceramide production and apoptosis. Thus, multiple lines of evidence suggest that maintenance of intracellular carnitine may be beneficial for cardiometabolic function.

1.4 Background Ingestion of Carnitine Varies by Diet.

A typical Western diet is high in meat and dairy intake and thus provides adequate carnitine ingestion to prevent depletion¹⁸. The Food and Nutrition Board has not established a recommended dietary allowance for carnitine and it is not considered an essential nutrient¹⁹. Nonetheless, relative carnitine deficiency develops in numerous inborn and chronic diseases, indicating that background ingestion is not sufficient to prevent depletion in some states^{13,18,20} and that normal plasma carnitine concentration may not be adequate for tissue needs depending on the demand²¹. This observation suggests that supplementation may be required to prevent or reverse depletion in at risk individuals despite normal dietary consumption. There are no published data on frequency of vegetarian or vegan diet in PAH that may predispose to deficiency or use of carnitine supplementation in this disease state.

1.5 Carnitine Supplementation in Humans

Given its safety and role in energy production, carnitine has been studied extensively and even touted as a performance enhancer for professional athletes. Although the liver and kidneys in a healthy human can metabolize the amino acids lysine and methionine to meet daily carnitine needs¹⁹, carnitine supplements are widely available. Carnitine supplementation has primarily been in the form of L-carnitine, or levocarnitine, which is the active form in the body²², that has a bioavailability of approximately 25%^{22,23}. After an oral dose of 30-100mg/kg body weight, peak plasma carnitine concentration occurs at 3-6 hours²⁴. In a study of the effect of long-term supplementation with L-carnitine, healthy adult men were fed similar doses (2g/day) of L-carnitine per day or placebo for 15 days. Subjects in the supplementation group maintained total plasma concentrations that were about 25 umol/L higher than in the control group, thus demonstrating the ability of carnitine supplementation to increase plasma carnitine over two weeks²². While there are no data on the effect of oral carnitine supplementation on cardiac carnitine content, a 2g/day oral L-carnitine supplement can modesty increase the skeletal muscle carnitine concentration by about 13% over four weeks²⁵. Carnitine supplementation has been tried in ageing, where it has had no effect on muscle strength²¹, however after acute myocardial infarction, a meta-analysis demonstrated that L-carnitine supplementation

reduced mortality, ventricular arrhythmias and angina over two months²⁶. L-carnitine can be metabolized by gut microbiota to proatherogenic trimethylamine-N-oxide (TMAO) which is associated with increased cardiovascular risk²⁷. However, limited prospective data exist to support this notion and none related to PAH or RV failure, which is not an atherosclerotic disease. Moreover, survival in PAH is generally fewer than 10 years²⁸, thus the relevance of TMAO to PAH is unclear.

2 Objectives and Specific Aims

